# **University of Kansas Medical Center**

## **RESEARCH PROTOCOL INVOLVING HUMAN SUBJECTS**

### **I. Purpose, Background and Rationale**

#### **A. Aim and Hypotheses**

Older adults are highly sedentary, spending more than 60% of waking time sitting. Independent of physical activity, daily sitting time is a risk factor for poor glycemic control and type 2 diabetes. Glycemic control and insulin sensitivity are inexorably linked to Alzheimer's disease (AD) and cognitive decline. Individuals with mild cognitive impairment (MCI) and AD display physiological differences in insulin and glucose regulation compared to older adults without cognitive impairment. Reducing sitting time and taking frequent breaks from sitting have resulted in improved glycemic control and insulin sensitivity within hours. Studies are beginning to suggest that time spent in seated activities (e.g., TV) is associated with poorer global cognitive function and risk of AD independent of physical activity.

The proposed study directly addresses the recommendations of an NIH sponsored workshop on "Physiology of Sedentary Behavior and its Relationship to Health Outcomes." 1) We will investigate the physiological correlates of sedentary behavior by assessing glycemic control and insulin sensitivity. 2) We will focus on the impact of lack of movement as distinct from the effects of movement by objectively measuring both simultaneously. In individuals with MCI, we will evaluate whether a behavioral intervention to reduce sitting can alter physiological processes known to contribute to disease pathology.

Cardiorespiratory fitness changes that occur with moderate or vigorous aerobic exercise may not be essential for improving brain health and cognition, as demonstrated by studies of activities that do not robustly improve fitness (Tai Chi, resistance training, Wii fit), but still show improvements in brain health and cognition. Even low intensity, non-exercise activity is associated with reduced risk of cognitive decline and healthier cardiometabolic measures. In fact, non-exercise activity accounts for the vast majority of daily activity, while exercise accounts for only 2-5%. More evidence is needed to determine whether reductions in sitting time are sufficient to produce changes in cognitive performance, brain volume, or neurogenesis as seen in aerobic exercise interventions.

Interventions targeting sedentary behavior can effectively reduce sitting time (average 42 min/day), but few studies have evaluated whether these reductions result in clinically meaningful outcomes and none have been conducted in older adults with MCI. **We propose a feasibility study of a 12-week home based behavioral intervention to reduce sitting time among sedentary older adults with MCI and their caregivers.** The intervention is designed to break up prolonged bouts of sitting and replace sitting behavior with standing and light or moderate intensity activities associated with improved cognitive performance among people at risk for AD. Our proposed intervention adds innovative elements that are empirically rigorous compared to previous studies: 1) it uses objectively assessed electronic postural monitoring, 2) it provides electronic feedback to promote sitting times <30 minutes, 3) it assesses insulin sensitivity and glycemic control which are sensitive to changes in sitting after a short duration and which few previous interventions have measured, 4) it is conducted in the home and targeted to individual habits and physical environments that reinforce sitting behaviors, 5) it targets sedentary older adults with MCI, which has not been done before, and 6) it capitalizes on the caregiver/patient dyad to help improve adherence to the behavioral change regimen.

**Specific Aim 1: Determine feasibility of a 12-week home and telephone based intervention in older adults with mild cognitive impairment targeting both the impaired individual and their study partner to help initiate and maintain behavior change.** We will recruit KUADC registry participants with MCI and their caregivers (as study partners). Behavioral interventions are more effective when there is built in social support. We will evaluate feasibility in terms of successful recruitment and retention of participants, 10% or less of technological failures, rate of participant concerns addressed by phone and at home visits, acceptability of the intervention to participants (measured by questionnaires during home visits).

**Specific Aim 2: Determine whether a 12-week home and telephone based intervention results in reduced total sitting time and shorter bouts of sitting in older adults with MCI and their caregivers.** Electronic postural monitors will record sitting time for a duration of one week at three time

points (pre-intervention, mid-intervention, and post-intervention). The intervention includes 1) feedback from baseline monitoring, 2) educational and goal setting session with the participants and research staff, 3) wrist worn monitors that alert wearers to sitting times >30 minutes, 4) home and telephone visits to address physical, psychological, and home environment barriers to behavior change. Changes in sitting time and breaks from sitting will be compared between baseline, mid-intervention, and post-intervention measurement occasions.

**Specific Aim 3: Determine whether sedentary behavior intervention results in improved insulin sensitivity and glycemic control.** To evaluate whether reduced sitting results in meaningful metabolic changes, we will measure postprandial insulin and glucose, and body composition, and evaluate changes from pre- to post- intervention adjusting for relevant covariates.

The PI is an early-career investigator who has completed KU-ADC funded pilot work using objective activity monitoring and has the necessary foundation for the proposed research on physical activity and sedentary behavior in older age and AD. She has several published papers on biomarkers associated with cognitive decline and dementia. She has successfully collaborated with the KU-ADC since 2008 to build a program of research measuring physical activity in naturalistic settings in older adults with and without AD. She has experience in use, interpretation, and analysis of objective activity monitoring data in ADC participants. Her pilot work found that participants with mild AD did not differ from older adult controls in their levels of moderate physical activity, but differed in sedentary and light intensity activities. This supports the idea that sedentary behavior is a valuable target for this population.

## **B. Background and Significance**

Older adults are highly sedentary, spending more than 60% of waking time sitting. Independent of physical activity, daily sitting time is a risk factor for poor glycemic control, unhealthy body composition, elevated lipid levels, and Type 2 diabetes. An NIH sponsored workshop identified research priorities and recommendations for understanding the "Physiology of Sedentary Behavior and its Relationship to Health Outcomes." The proposed study addresses these recommendations directly. 1) We investigate the physiological correlates of sedentary behavior by assessing glycemic control and insulin sensitivity. 2) We focus on the impact of lack of movement as distinct from the effects of movement by accurately and objectively measuring both simultaneously. In individuals with mild cognitive impairment (MCI), we will evaluate whether a behavioral intervention can alter physiological processes that contribute to disease pathology.

Glycemic control and insulin sensitivity are highly modifiable through changes in activity and sitting and are inexorably linked to Alzheimer's disease (AD) and cognitive decline. Individuals with MCI and AD display physiological differences in insulin and glucose regulation compared to older adults without cognitive impairment. Reducing total sitting time and taking frequent breaks from sitting have resulted in improved glycemic control and insulin sensitivity. Reduced insulin sensitivity has been shown to occur within hours after a transition to sedentary behavior. Time spent in seated activities (e.g., TV) is associated with poorer global cognitive function and risk of AD independent of physical activity.

Cardiorespiratory fitness changes that only occur with moderate or vigorous aerobic exercise may not be essential for improving brain health and cognition, as demonstrated by studies of activities that do not robustly improve fitness (Tai Chi, resistance training, Wii fit), but still show improvements in brain health and cognition. Even low intensity, non-exercise activity is associated with reduced risk of cognitive decline and healthier cardiometabolic measures. In fact, non-exercise activity accounts for the majority of daily activity, while exercise accounts for only 2-5%. More evidence is needed to determine whether reductions in sitting time are sufficient to produce changes in cognitive performance and neuroanatomy as seen in aerobic exercise interventions.

A recent meta-analysis reports that interventions targeting sedentary behavior can effectively reduce sitting time in adults (average 42 min/day), but few studies have evaluated whether these reductions result in clinically meaningful health outcomes. Furthermore, few interventions have been conducted in older adults. One intervention to reduce sitting time in older adults included one on one goal setting and individualized feedback on objectively derived sitting time. Participants successfully reduced sitting time, increased breaks in sitting, and increased light and moderate intensity activities. Our 12 week intervention

adds new elements to strengthen this design: 1) objective *postural* monitoring, 2) electronic reminders when sitting >30 minutes (real time reminders are more effective than education alone in reducing sitting), 3) assessment of insulin sensitivity and glycemic control which are sensitive to changes in sitting after a short duration.

The proposed intervention is ecologically valid—it can be done in any setting. It uses participants' goals and preferences to guide behavior changes instead of defining goals for them. The intervention is designed to break up bouts of prolonged sitting and replace sitting behavior with standing, light and moderate intensity activities (e.g., walking, household activities, and resistance exercise) which have been associated with improved cognitive performance among people at risk for AD.

**Preliminary Results:** The PI is an early-career investigator with a foundation for the proposed research on physical activity, sedentary behavior, and associated biomarkers in older age and AD. Pilot research allowed us to establish expertise in use, interpretation, and analysis of activity monitoring data. In 100 participants, we had excellent retention (99%) and low rates of technological problems that prevent valid data collection (5%). We found that participants with mild AD did not differ from older adult controls in their levels of moderate physical activity, but differed in sedentary and light intensity activities. This supports the idea that sedentary behavior is a valuable target for this population. We discovered that patterns of activity variability differ between men and women (i.e., women are more consistently active across days), but did not differ by dementia status. Understanding within-individual variability helps target interventions toward individual habits to result in tailored behavior change approaches. We conducted a focus group with the KU-ADC Ambassadors and consulted with experts ([name], [name], [name], [name], & [name]) to develop our intervention.

### **C. Rationale**

Our proposal is innovative in 6 ways compared to previous studies: 1) it is conducted in the home and targeted to individual habits and physical environments that reinforce sitting behaviors, 2) it uses objectively assessed electronic postural monitoring, 3) it provides electronic reminders to reduce sitting, 4) it targets sedentary older adults with MCI, which has not be done before, 5) it assesses glycemic control and insulin sensitivity which are sensitive to changes in sitting after a short duration and which few previous interventions have measured, and 6) it capitalizes on the caregiver/patient dyad to help improve adherence to the behavioral change regimen.

## **II. Research Plan and Design**

### **A. Study Objectives:**

We propose a **feasibility** study of a 12-week home based behavioral intervention to reduce sitting time among sedentary older adults with MCI and their caregivers.

### **B. Study Type and Design:**

The proposed pilot study will include individuals with MCI and their caregivers as a dyad. We will use a multi-level model to evaluate the change in our outcome variables across three time points. Level 1 is time of observation (baseline, mid-study, follow up). Level 2 is the individual (with or without MCI), and Level 3 is the level of the dyad. This model includes the non-independence in the estimation of the two members of the dyad as well as repeated observations for each individual. This model also allows us to compare whether individuals with MCI are equally or less responsive to the intervention than the study partners within the context of the dyadic relationship. Future funding applications will include an RCT design with a control group of dyads who do not receive the intervention or a double baseline design to establish within person change with and without the intervention. We chose an intervention duration of 12 weeks. A previous intervention study in middle-aged adults observed changes in glucose and insulin within 2 hours of reduced sitting replaced by light walking. A 6-month intervention in adults improved insulin levels and waist circumference.

## Sample Size, Statistical Methods, & Power

We will enroll 15 dyads of older adults (N=30 individuals; 15 with MCI and 15 non-impaired caregivers).

Aim 1: We will evaluate feasibility in terms of 1) successful recruitment and retention of participants, specifically how many months did it take to recruit an adequate sample of participants, 2) 10% or less of technological failures, calculated as the number of failures divided by the total number of participants enrolled, 3) rate of participant concerns addressed by phone and at home visits, as measured by numerical counts of concerns successfully or unsuccessfully addressed and percent of participants having concerns, and 4) acceptability of the intervention to participants (measured by questionnaires during home visits), we will describe these data using descriptive statistics.

Aims 2 and 3: Our proposal is underpowered to detect significant effects, however we will focus on finding a meaningful effect size for the treatment (which is not affected by sample size). We feel this is acceptable given the **feasibility** focus of our pilot study. A previous RCT of an intervention to reduce sitting in multiple sclerosis reported a statistically significant main effect, Cohen's  $d = 0.49$ , for intent-to-treat analysis.

We will use a multi-level model to evaluate the change in our outcome variables across three time points. Level 1 is time of observation (baseline, mid-study, follow up). Level 2 is the individual (with or without MCI), and Level 3 is the level of the dyad. This model includes the non-independence in the estimation of the two members of the dyad as well as repeated observations for each individual. This model also allows us to compare whether individuals with MCI are equally or less responsive to the intervention than the study partners within the context of the dyadic relationship. Constraining estimates to be equivalent provides a test of the significance of the difference in the estimates between the MCI patients and the study partners. We are primarily interested in the change in outcome measures (listed below) from pre-intervention to post-intervention (i.e., is the intervention effective), thus we are testing for a growth model with an intercept change, indicating a mean change after the intervention, this type of model can estimate discontinuous processes with longitudinal data. With regard to the multiple time points, we hypothesize an improvement in outcomes from baseline to mid-point and a maintenance effect from mid-point to follow up. Outcomes are (1) average daily sitting time (2) number of sitting bouts  $>30$  min (3) insulin and glucose, adjusting for baseline values and relevant covariates (disability status, medications, age, education, etc.). Data will be validated for wear time (i.e. remove periods of sleep or monitor removal). A valid day of wear is  $\geq 10$  hours of waking wear time and a valid week of wear includes  $\geq 4$  valid days of wear ( $\geq 1$  weekend day).

**D. Participant criteria.** We will enroll 15 dyads of older adults (N=30 individuals; 15 with MCI and 15 non-impaired caregivers) per Table 1 criteria. We will recruit additional participants in the event of screen failure or technological problems to reach our enrollment goal. MCI status will be determined by CDR in the most recent KU Alzheimer's disease center (ADC) Registry visit (See Appendix I: Vulnerable Populations). Inactive status will be determined by the Measure of Older Adults' Sedentary Time (MOST), a 7-item questionnaire about sitting activities common in older adults. There is no guidance from the literature for cutoffs for self-reported sitting times. Self-reports consistently underestimate sitting times compared to objective measures and we do not wish to exclude the majority of individuals screened. Thus, we will use a cutoff of self-reported sitting time of  $\geq 7$  hours per day not counting time spent sleeping or napping. This is roughly the average time spent sitting per self-reports using this questionnaire in a previous study of older adults ([name] et al. 2011). The MOST scale can be found in Appendix II. We will include individuals with glucose in the normal or pre-diabetic range. No participant who is eligible to participate based on inclusion/exclusion criteria will be denied based upon race, gender, or ethnicity.

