## E. Methods

### Measures

**Sitting.** Our primary outcome measures are the average number of minutes sitting per day and the number of sitting bouts  $>30$  minutes during waking hours over one week measured with activPAL (PalTechnologies, Glasgow, Scotland). ActivPAL is superior in estimation of postural changes (sitting vs. standing) compared to other monitors partly due to thigh placement. It is waterproofed for 7+ days by placing in a nitrile sleeve and wrapping in medical adhesive before attaching to the thigh with medical adhesive (i.e., can be worn while bathing). The device estimates time in sitting, standing, or stepping postures and transitions (sit-to-stand, stand-to-sit) in 15 second epochs. It is small, lightweight, and unobtrusive. Its rechargeable batteries last up to 14 days. We have successfully collected pilot data from 100 older adults establishing safety and **feasibility** including adhesive integrity for the study duration. Participants will be educated on use of the device before recording data. Logs will be used to record waking/sleeping times and problems with or removal of monitors (see appendices).

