## **V. Data Analysis and Reporting**

### **Statistical and Data Analysis:**

**Data Analysis:** We will use a multi-level model to evaluate the change in our outcome variables across three time points. Level 1 is time of observation (baseline, mid-study, follow up). Level 2 is the individual (with or without MCI), and Level 3 is the level of the dyad. This model includes the non-independence in the estimation of the two members of the dyad as well as repeated observations for each individual. This model also allows us to compare whether individuals with MCI are equally or less responsive to the intervention than the study partners within the context of the dyadic relationship. Constraining estimates to be equivalent provides a test of the significance of the difference in the estimates between the MCI patients and the study partners. We are primarily interested in the change in outcome measures (listed below) from pre-intervention to post-intervention (i.e., is the intervention effective), thus we are testing for a growth model with an intercept change, indicating a mean change after the intervention, this type of model can estimate discontinuous processes with longitudinal data. With regard to the multiple time points, we hypothesize an improvement in outcomes from baseline to mid-point and a maintenance effect from mid-point to follow up. Outcomes are (1) average daily sitting time (2) number of sitting bouts >30 min (3) insulin and glucose, adjusting for baseline values and relevant covariates (disability status, medications, age, education, etc.). **Outcome:** Milestones for achieved **feasibility** include successful recruitment and retention of participants, 10% or less of technological failures, rate of participant concerns addressed by phone and at home visits, acceptability of the intervention to participants (measured by questionnaires HI3), and few adverse events. Effectiveness of the intervention will be evaluated based on change of moderate effect size in the average amount of time spent in sitting and duration of sitting bouts as demonstrated in previous studies. Two previous intervention studies reported a decline in sitting time of about 3 - 4%. We will use this range as our target for success.

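### The plan reads an uncontrolled pre-to-post change as intervention effectiveness, which a single-arm design with one baseline week cannot show

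*Combined protocol and SAP*

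**What the plan says.** Under Sample Size, Statistical Methods, & Power, the protocol names its main interest as the "change in outcome measures (listed below) from pre-intervention to post-intervention (i.e., is the intervention effective"). Section V, Statistical and Data Analysis, repeats this and describes the model: "thus we are testing for a growth model with an intercept change, indicating a mean change after the intervention".

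Section V then gives two criteria. The first is "Effectiveness of the intervention will be evaluated based on change of moderate effect size in the average amount of time spent in sitting", together with the duration of sitting bouts. The second rests on earlier work: "Two previous intervention studies reported a decline in sitting time of about 3 - 4" percent, followed by "We will use this range as our target for success". The power section also speaks of a meaningful effect size for the treatment, and Aims 2 and 3 ask whether the intervention results in the changes.

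On design, every dyad is treated and Table 2 shows one baseline monitoring week. Section II.B leaves comparison to later work: "Future funding applications will include an RCT design with a control group of dyads who do not receive the intervention". For the same later work it names one alternative to such a trial: "or a double baseline design to establish within person change with and without the intervention".

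**The concern.** A change from before to after treatment in one treated group is the sum of the intervention effect and whatever would have happened anyway. Table 2 puts baseline monitoring at week 0 and follow-up monitoring at week 13, so season and ordinary time trend can enter, as can a different reaction to the first monitored week than to later ones. The analysis plan has no term or comparison that separates these from the intervention.

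The plan's caveat is that it is underpowered. That is about precision. A larger sample would narrow the interval around the same mixed quantity and leave the bias in place.

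The stake is what the pilot can claim. Its results are to be published and to support an application for a larger randomised trial. If Section V is followed as written, a fall of 3-4% would count as success on effectiveness, a causal reading that the design does not support.

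**Working it through.** **Is there a control hidden in the design?**

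- The comparison of people with MCI and their partners is not one, because both members receive the visits, calls and wrist alerts (Procedures).
- The mid-study week is a partial safeguard. Improvement by week 6 followed by maintenance differs from steady drift. It does not rule out a one-time shift between the first monitored week and the later ones. Table 2 schedules insulin and glucose only at the two clinic visits, so those outcomes have no mid-point at all.
- Section II.B names two designs that would separate change with and without the intervention, and places both in future applications.

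**How small is the target against chance and drift?** The plan gives no SD of change, baseline mean, partner correlation, alpha or power, so there is no figure of its own to reproduce. The following illustrates scale only.

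From the documents: 15 dyads (30 people) and a target of 3-4%. Assumed: baseline sitting 540-660 min/day, SD of individual change 60-90 min/day, correlation of change between partners 0.3, and non-intervention drift of 0, 10 or 20 min/day in either direction.

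1. Standard error of the mean change over 15 pairs: SE = SD × √((1 + 0.3)/30) = SD × 0.208. This gives 12.5 min/day for SD 60 and 18.7 for SD 90.
2. The 3% target in minutes: 0.03 × 540 = 16.2 to 0.03 × 660 = 19.8. That is 0.9 to 1.6 SE (16.2/18.7 and 19.8/12.5).
3. Chance of an observed fall of at least 3% with no intervention effect: P = 1 − Φ((0.03 × baseline − drift)/SE), where a positive drift is a fall in sitting.

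| Non-intervention drift | Chance of meeting 3% |
|---|---|
| 20 min/day fall | 50-62% |
| 10 min/day fall | 22-37% |
| none | 6-19% |
| 10 min/day rise | 1-8% |
| 20 min/day rise | under 3% |

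Worked end points with no drift: baseline 660 and SD 60 give 1 − Φ(1.59) = 6%; baseline 540 and SD 90 give 1 − Φ(0.86) = 19%. The 20 min/day fall is at least as large as the target (16.2-19.8), so a chance above one half follows by construction and adds little.

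4. The other criterion. The plan does not say how a moderate effect size is standardised. If it means 0.5 SD of change (an assumption), P = 1 − Φ((0.5 × SD − drift)/SE). With no drift this is 1 − Φ(0.5/0.208) = 1 − Φ(2.40) = 0.8%. With a 10 min/day fall it is 3-5%, and with a 20 min/day fall 9-21%. On the same inputs the 3% target is only 0.18-0.33 SD (16.2/90 to 19.8/60), so it is much the easier of the two to meet.

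**The case against.** The best defence is that this is openly a feasibility pilot. The power section calls Aims 2 and 3 underpowered, Section II.B points to controlled designs as the next step, and the milestones in Section V concern recruitment, retention, technology, participant concerns, acceptability and adverse events. No documented go/no-go decision turns on efficacy. This stands as a limit on severity: the feasibility aim is unaffected, and a pilot need not become a randomised trial. It does not rescue the effectiveness criteria, which Section V sets out separately from the milestones.

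Three stronger readings are tempting, and the documents do not support them.

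- A reader might infer that the plan admits a control is needed. Section II.B says only that future applications will include one, or a double baseline. The recognition is implicit.
- A reader might infer that the bias favours the intervention. Season and trend can go either way, and reactivity that lowers sitting in the first monitored week would shrink the observed fall. The documents give neither size nor direction. The higher chances in the table also apply only to the 3% target, not to the moderate-effect criterion.
- Because of the monitor, "Its rechargeable batteries last up to 14 days", a reader might infer that a second baseline week would supply the missing double baseline. Two adjacent weeks could show early reactivity, but not season or drift over roughly 13 weeks. The protocol specifies seven days of wear, and a second week would add burden.

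**Conclusion.** The point holds as a mismatch between claim and design. The planned contrast estimates within-person change, and the plan labels it effectiveness. This follows from the text and needs no assumed number: one treated group, one baseline week, no comparison, and a caveat that addresses only precision.

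The size of any bias cannot be derived from the documents. On the assumptions stated, meeting the 3% target with an ineffective intervention ranges from 1-8% (10 min/day rise) through 6-19% (no drift) to 22-37% (10 min/day fall). These figures show that the target is small beside plausible noise and drift. They do not predict that the pilot will report a false success, and they do not invalidate its sample, model or feasibility aim.

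**What to change.** In the power section and Section V, replace the wording that equates pre-to-post change with effectiveness. State that the quantity estimated is within-person pre-to-post change, which may include change unrelated to the intervention. Report it with a 95% confidence interval, and say that it cannot by itself be attributed to the intervention. Treat the power section's effect size for the treatment in the same way, as a standardised within-person change.

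The 3-4% figure may stay as a descriptive benchmark or a progression signal for the later randomised trial, but not as evidence of effectiveness.

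The cost is a text amendment and a confidence interval that the planned model already yields. Sample, visits, monitoring schedule and model stay as they are. No second baseline week is recommended.
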